2.4.2.1 ICS in combination with other controllers

ICS and other asthma controller medications will be identified as the medications reported on the 'Prescribed Asthma Controller Medications' eCRF page.

Prior asthma controller medications will be summarized by treatment group sorted by decreasing frequency of standard medication name on the incidence in the overall treatment group.

Concomitant asthma controller medications will be summarized by treatment group sorted by decreasing frequency of standard medication name on the incidence in the dupilumab group.

The total daily dose of ICS in asthma controller medication at randomization will be classified as medium-dose or high-dose according to [Appendix C](#). If a patient takes more than one medication containing ICS, the ICS dose of different products will be standardized according to equivalent dose specified in [Table 5](#). The equivalent dose is determined based on the thresholds in [Appendix C](#). After conversion, the total daily dose for inhaled corticosteroid will be calculated and classified as medium or high dose.

Table 5 - Equivalent dose for inhaled corticosteroids for children (≥6-11 years)

Inhaled corticosteroid	Conversion Factor to Fluticasone propionate (DPI)		
	Low	Medium	High
BECLOMETASONE DIPROPIONATE (CFC)	1	1	1
BECLOMETASONE DIPROPIONATE (HFA)	2	2	2
BUDESONIDE (DPI)	1	1	1
BUDESONIDE (HFA)	1	1	1
BUDESONIDE (nebulas)	0.4	0.4	0.4
CICLESONIDE (HFA)	2.5	2.5	2.5
FLUNISOLIDE (HFA)	1.25	1.25	1.25
FLUTICASONE PROPIONATE(HFA)	1	$(200+x*2)/3$	0.8
MOMETASONE FUROATE	10/11	10/11	10/11
TRIAMCINOLONE ACETONIDE	0.25	$-200+x/2$	1/3

HFA=hydrofluoroalkane, DPI= Dry Powder Inhaler

x: the actual dose level of the corresponding inhaled corticosteroid

Example:

1): when the dose of FP(HFA) is 500 mcg, the corresponding dose of FP(DPI) will be $200/3 + 500*2/3=400$ mcg.

2): when the dose of TRIAMCINOLONE ACETONIDE is 1200 mcg, the corresponding dose of FP(DPI) will be $(-200 + 1200/2) = 400$ mcg.

2.4.2.1.1 Compliance

During the study, the daily intake of each prescribed asthma controller medication will be recorded on the electronic diary every evening. Compliance for the controller medications with ICS component and overall compliance to all prescribed controller medications will be calculated for each patient. For each day, a patient is considered as compliant to the prescribed controller medication with ICS component if the actual dose of each controller medication with ICS component is same as or greater than the prescribed dose. Similarly, a patient is considered as compliant to all controller medication if the actual dose of each controller medication is same as or greater than the prescribed dose. Note that if the prescribed dose has been stepped-up based on protocol specified criteria, the compliance post dose increase will be calculated based on the updated prescribed controller medication dose.

Compliance for controller medication(s) with ICS component is defined as the **number of days** when the patient is compliant to the prescribed controller medication(s) with ICS component divided by the number of days the patient stays in the treatment period (from first dose to last dose + 14 days). **Overall controller medication(s) compliance** is defined as the **number of days** when the patient is compliant to all prescribed controller medication divided by the number of days the patient stays in the treatment period. Since it is required by the protocol that a 12 hours washout is required before spirometry tests, the calculation of overall controller medication compliance for patients with prescribed LABA will exclude the data from the spirometry test days.

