7.2.2 Exclusion Criteria Related to the Active Comparator and/or Mandatory Background Therapies

- E 14. Non-compliance with use of the mandatory background therapy (ie, medium-dose ICS with a second controller medication [eg, LABA, LTRA, LAMA, or methylxanthines] or high-dose ICS alone or high-dose ICS with second controller), during the Screening Period, as defined as <80% of total number of prescribed doses of background medication taken during the Screening Period. Compliance is verified based on background medication use recorded on the patient electronic diary during the Screening Period.
- E 15. Patient treated with SCS for diagnoses other than severe exacerbation of asthma, and/or high-potency topical steroids within 30 days before Screening Visit 1, during the Screening Period, and/or during the randomized treatment phase of this study.
- E 16. Patient with history of clinically significant renal, hepatic, cardiovascular, metabolic, neurologic, hematologic, ophthalmologic, respiratory, gastrointestinal, cerebrovascular or other significant medical illness or disorder which, in the judgment of the Investigator, could interfere with the study or require treatment that might interfere with the study. Specific examples include but are not limited to uncontrolled diabetes, active hepatitis, active or latent untreated tuberculosis, bronchiectasis. Patients with active tuberculosis, latent untreated tuberculosis or a history of incompletely treated tuberculosis will be excluded from the study unless it is well documented by a specialist that the patient has been adequately treated and can now start treatment with a biologic agent, in the medical judgment of the Investigator and/or infectious disease specialist. Tuberculosis testing will be performed in every country according to their local guidelines as required by regulatory

authorities and/or ethic committees. Other conditions that are well controlled and stable will not prohibit participation if deemed appropriate per the Investigator's judgment.

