9.2.2.1 Disease-specific Efficacy Measures

9.2.2.1.1 Spirometry

A spirometer that meets the 2005 American Thoracic Society (ATS)/European Respiratory Society (ERS) recommendations will be used. Spirometry should be performed in accordance with the ATS/ ERS guidelines (8). For pre-bronchodilator measured parameters, including FEV₁, peak expiratory flow (PEF), FVC and FEF 25-75%, spirometry will be performed after a wash out period of bronchodilators according to their action duration, for example, withholding the last dose of salbutamol/albuterol or levosalbutamol/levalbuterol for at least 6 hours, withholding the last dose of LABA for at least 12 hours, and withholding the last dose of LAMA for at least 24 hours. This will be verified before performing the PEF measurements.

For post-bronchodilator FEV₁, the measure should follow the steps as that at screening test for reversibility validation.

At all visits, spirometry will be performed either in the AM or PM, but preferred in the AM, and the spirometry should be done at approximately the same time at each visit throughout the study. The same spirometer and standard spirometric techniques, including calibration, will be used to perform spirometry at all visits and, whenever possible, the same person should perform the measurements.

Pulmonary function tests will be measured in sitting position; however, if necessary to undertake the testing with the subject standing or in another position, this should be noted on the spirometry report. For any subject, the position should be consistent throughout the study.

Three measurements fulfilling the ATS acceptability and repeatability criteria should be obtained at every visit, if possible. The acceptability criteria must be applied before the repeatability criteria. Unacceptable maneuvers must be discarded before applying the repeatability criteria. If a subject fails to provide repeatable and/or acceptable maneuvers, an explanation should be recorded.

The largest FEV1 and largest FVC should be recorded after the data are examined from all of the acceptable curves, even if they do not come from the same curve. The FEF 25-75% should be obtained from the single curve that meets the acceptability criteria and gives the largest sum of FVC plus FEV1 (best test).

Automated best efforts, which combine FEV1 and FVC are not acceptable.

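### The SAP's spirometry-day exclusion covers only LABA and only overall controller compliance, so required washouts can count as non-compliance for LAMA users (overall) and ICS/LABA users (ICS component)

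*SAP*

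**What the plan says.** SAP 2.4.2.1.1 builds both measures from the e-diary, in which "the daily intake of each prescribed asthma controller medication will be recorded on the electronic diary every evening". For the ICS-component measure, a day is compliant "if the actual dose of each controller medication with ICS component is same as or greater than the prescribed dose". The overall measure applies the same daily test to every prescribed controller, with or without an ICS. The count of compliant days is then "divided by the number of days the patient stays in the treatment period (from first dose to last dose + 14 days"; the overall measure uses the same denominator.

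One adjustment follows. The SAP gives as its reason that "a 12 hours washout is required before spirometry tests", and on that ground states that "the calculation of overall controller medication compliance for patients with prescribed LABA will exclude the data from the spirometry test days". It does not mention LAMA and makes no matching exclusion in the ICS-component measure. It also does not say whether the excluded days leave the denominator as well as the numerator.

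The washout in Protocol 9.2.2.1.1 is wider: it describes "withholding the last dose of LABA for at least 12 hours, and withholding the last dose of LAMA for at least 24 hours". Protocol 8.2.1 accepts LAMA as a second controller and permits only one second controller. Appendix B of the protocol and Appendix B of the SAP both list ICS/LABA combination products.

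**The concern.** The SAP accepts a sensible principle: a dose withheld because the protocol requires it should not count against the child. It then applies that principle to one drug class in one measure. Two like cases are left out.

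- **LAMA, overall measure.** A child whose second controller is LAMA is not a LABA patient, because only one second controller is allowed. That child never receives the exclusion, although the protocol's interval for LAMA is the longer of the two.
- **ICS/LABA combination inhaler, ICS-component measure.** These children have a prescribed LABA, so their test days already leave overall compliance. The ICS-component measure removes no days, yet the ICS in a combined inhaler is withheld together with the LABA.

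The second case also makes the two measures inconsistent with each other. Overall compliance requires every controller to be taken, so on a common set of days it cannot exceed ICS-component compliance. Under the written rule it can.

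What is at stake is the descriptive account of background adherence. Differences between controller classes, or between the two measures, could reflect the counting rule and not what the children took.

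**Working it through.** The documents state no controller-compliance percentage, so there is no figure to reproduce. The check is a count of days.

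**Inputs**

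- Spirometry visits: Protocol 10.1.3 to 10.1.13 place spirometry at Weeks 0, 2, 4, 6, 8, 10 and 12 (7 days) and at Weeks 16, 20, 24, 28, 32, 36, 40, 44, 48 and 52 (10 days). The ten visits for study-drug administration only (Weeks 14, 18, 22, 26, 30, 34, 38, 42, 46 and 50, Protocol 10.1.9) have none. Total: 7 + 10 = 17, or 16 after Day 1.
- Treatment period: first dose on Day 1. The last scheduled dose is at Week 50, which is Day 1 + 50 × 7 = 351. Adding 14 days gives Day 365, so there are 365 days counted inclusively.
- Daily test: the day's actual dose must be at least the prescribed dose.

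**Formula**

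Compliance = compliant days / days in the treatment period. Take a child who is otherwise fully adherent and falls short on a fraction *f* of the test days. The loss is *f* × 17/365, or *f* × 16/365 if Day 1 is not affected. The documents do not give *f*, so the whole range is shown.

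| *f* (assumed) | Loss, 16 days | Loss, 17 days |
|---|---|---|
| 0 (every dose made up the same day) | 0 | 0 |
| 0.5 | 8/365 = 2.2 points | 8.5/365 = 2.3 points |
| 1 (no dose made up) | 16/365 = 4.4 points | 17/365 = 4.7 points |

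The worst case is therefore 349/365 = 95.6% or 348/365 = 95.3%.

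**Who is affected, at *f* = 1 with 17 days**

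| Background therapy | Overall compliance | ICS-component compliance |
|---|---|---|
| ICS plus LAMA | 348/365 = 95.3% | 100% (ICS not withheld) |
| ICS plus LABA, separate inhalers | 348/348 = 100% | 100% (ICS not withheld) |
| Single ICS/LABA combination inhaler | 348/348 = 100% | 348/365 = 95.3% |

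The last row is the inconsistency. One inhaler and one diary give 100% for all controllers and 95.3% for the ICS in that same inhaler. The 100% assumes that excluded days leave the denominator too. If they left only the numerator, the LABA user would also score 348/365 = 95.3% and the exclusion would achieve nothing, so the wording needs to settle this.

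**Scope of the bound.** It is for a child who completes treatment. Tests are two-weekly up to Week 12, so the share is larger for a child who stops early. For example, a last dose at Week 10 (Day 71) gives a period to Day 85 containing 7 test days, and 7/85 = 8.2%.

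**The case against.** The strongest reply is that a washout does not by itself make a day non-compliant. The diary is completed in the evening, and Protocol 9.2.2.1.1 prefers spirometry in the morning. The protocol asks for the last dose to be withheld for a minimum interval, not for a day's dose to be skipped. A dose taken after the test keeps the day compliant. This stands: 95.3% is a worst case, and a reader should not infer that every test day is scored as a failure. But the SAP itself judged test days unreliable enough to remove for LABA users, and its reason applies equally to the two cases left out.

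The second reply is that little depends on the measure. This also stands. No efficacy model, estimand, analysis population or test is stated to use controller compliance, and SAP Appendix M has no row for it. Permanent step-ups of controller therapy are summarised separately (SAP 2.4.2) and handled in the treatment-adherence estimand (SAP 2.4.4.1). The washout rules are the same in both randomised, blinded arms, so there is no evident route to a difference between arms.

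Three stronger readings are tempting, and the documents do not support them.

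- **Days without a diary entry are scored as missed doses.** The SAP does not say how such days are scored, so this is an inference from silence. Keeping all days in the denominator is a defensible, conservative choice.
- **The result should be comparable with exclusion criterion E 14.** That criterion concerns "<80% of total number of prescribed doses of background medication taken during the Screening Period", which is a share of doses used for eligibility. The SAP sets no such threshold for controllers during treatment and makes no such comparison.
- **The day before each test should also be excluded.** A washout may reach into it, but identifying those days needs dose times. The diary is described as recording inhalations per day (Protocol 9.2.2.2.1, SAP 2.1.3.4.1).

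**Conclusion.** The point holds as an inconsistency in a stated rule. Required washouts can count as non-compliance for LAMA users in overall compliance and for ICS/LABA combination users in ICS-component compliance. They cannot do so for LABA users in overall compliance, provided excluded days leave both parts of the ratio.

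The size is at most about 4.4 to 4.7 percentage points for a child who completes treatment, and nothing for a child who makes up each withheld dose the same day. This rests on the scheduled visits, full treatment and otherwise complete adherence, and it counts test days only. The effect on a group mean cannot be computed, because the documents do not give the share of children on LAMA or on combination inhalers.

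A reader might infer that the trial's background therapy was less stable than claimed, or that the efficacy results are affected. Neither follows, because this is a descriptive summary that no efficacy analysis is stated to use. It is a minor clarification worth making. No position is taken on the washout intervals themselves.

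**What to change.** Amend SAP 2.4.2.1.1 as follows:

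1. In overall controller compliance, exclude spirometry test days for patients prescribed LABA or LAMA.
2. In ICS-component compliance, exclude spirometry test days for patients on ICS/LABA combination products.
3. State that excluded days leave both the numerator and the denominator.
4. Give the reason as the protocol's washout for both LABA and LAMA, so that the SAP's 12-hour statement and Protocol 9.2.2.1.1 are reconciled.

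Optionally, report diary completion beside the compliance figures so that readers can see how much data lies behind them.

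The cost is a few sentences and minor reprogramming, with no change to visits, washouts or data collection. The downside is that slightly fewer days contribute: for the patients concerned, 365 − 17 = 348 of 365.

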2.4.3 Extent of investigational medicinal product exposure and compliance

The extent of IMP exposure and compliance will be assessed and summarized by actual treatment for Safety population, population with Type 2 inflammatory asthma phenotype, and population with baseline blood eosinophils ≥ 0.3 Giga/L ([Section 2.3.1](#)).

2.4.3.1 Extent of investigational medicinal product exposure

The extent of IMP exposure will be assessed by the duration of IMP exposure.

Duration of IMP exposure is defined as last dose date – first dose date + 14 days, regardless of unplanned intermittent discontinuations (see [Section 2.5.3](#) for calculation in case of missing or incomplete data).

Duration of IMP exposure will be summarized descriptively as a quantitative variable (number, mean, SD, median, minimum, and maximum). In addition, duration of treatment exposure will also be summarized categorically by numbers and percentages for each of the following categories and cumulatively according to these categories:

- >0 and ≤ 2 weeks
- >2 and ≤ 4 weeks
- >4 and ≤ 8 weeks
- >8 and ≤ 12 weeks
- >12 and ≤ 16 weeks
- ...
-
- >48 and ≤ 52 weeks
- >52 weeks

Additionally, the cumulative duration of treatment exposure will be provided, defined as the sum of the duration of treatment exposure for all patients, and will be expressed in patient years.

2.4.3.2 Compliance

A given administration will be considered noncompliant if the patient did not take the planned dose of treatment as required by the protocol. No imputation will be made for patients with missing or incomplete data.

Percentage of compliance for a patient will be defined as the number of administrations that the patient was compliant divided by the total number of administrations that the patient was planned to take during the treatment epoch defined in [Section 2.1.4](#).

Above-planned dosing percentage for a patient will be defined as the number of administrations that the patient took a higher dose than planned divided by the total number of administrations that the patient was planned to take during the treatment epoch.

Under-planned dosing percentage for a patient will be defined as the number of administrations that the patient took a lower dose than planned divided by the total number of administrations that the patient was planned to take during the treatment epoch.

Treatment compliance will be summarized descriptively as quantitative variables (number, mean, SD, median, minimum, and maximum). The percentage of patients whose compliance is <80% will be summarized. In addition, numbers and percentages of patients with at least 1 above-planned dose administration will also be provided, as well as numbers and percentages of patients with 0, (0, 20%], and >20% underplanned dose administrations.

Cases of overdose of IMP (defined as at least twice the intended dose during an interval of less than 11 days) will be summarized by numbers and percentages of patients with at least 1 over dose by treatment group. Different overdose intense by dose interval, ie, 1 day, 2 days, etc., will also be summarized. More generally, dosing irregularities will be listed as being described in [Section 2.2.1](#).

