k Electronic diary/PEF meter is used for daily recording of salbutamol/albuterol or levosalbutamol/levalbuterol use, asthma controller drug use, oral steroid requirements, nocturnal awakenings due to asthma symptoms requiring the use of reliever medications, morning and evening asthma symptom NRS scores and AM and PM PEF. This device is dispensed at Visit 1 and information is downloaded from this device on the other indicated days.

l During the Randomized Treatment Period IMP administrations, every 2 week (q2w), will be performed by the Investigator at scheduled study site visits (must be separated by at least 11 days) up to Week 50. In the first 12 weeks (up to V8), patients will be monitored at the study site for a minimum of 30 minutes after injection of IMP, to assess any injection reactions (see [Section 8.1.4](#) for more details). After randomization, dose regimen will not be adjusted for patient's age or weight until the randomized treatment will be completed.

m Home Dosing and training of parent(s)/caregiver(s)/legal guardian(s): For all visits scheduled only for IMP administration (ie, at Weeks 14, 18, 22, 26, 30, 34, 38, 42, 46, and 50), parent(s)/caregiver(s)/legal guardian(s) may decide to do the injection of IMP at home (ie, home administration of IMP). These parent(s)/caregiver(s)/legal guardian(s) will be trained by the Investigator or designee to administer IMP, by demonstration at V2, V3, and V4 (injections performed by Investigator). After parent(s)/caregiver(s)/legal guardian(s) have successfully administered IMP under close supervision of the Investigator at V5-V8 (Weeks 6, 8, 10, and 12), the Investigator may approve them to perform home administration of IMP at all further visits that do not require a scheduled visit. It is possible to start home administration at any visit following V9, provided parent(s)/caregiver(s)/legal guardian(s) have been trained by the investigator or designee to administer IMP by demonstration at not less than 3 visits followed by a successful IMP administration under close supervision of the investigator or designee at not less than 3 visits.

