8.1.4 Dosing schedule

The IMP is administered every 14 ± 3 days q2w. The doses of investigational product must be separated by ≥ 11 days to avoid overdose.

The IMP administrations will be performed by the Investigator or designee at scheduled study site visits following clinic procedures and blood collection (see [Section 1.2](#)). Patients will be monitored for a minimum of 30 minutes after each study-site administrated injection of IMP, to assess any injection site reactions (eg, for any signs or symptoms of a hypersensitivity reaction).

For all visits scheduled only for IMP administration, parent(s)/caregiver(s)/legal guardian(s) may decide to do the injection of IMP at home (ie, home administration of IMP). These parent(s)/caregiver(s)/legal guardian(s) will be trained by the Investigator or designee to administer IMP, by demonstration at Visit 2, Visit 3, and Visit 4 (injections performed by Investigator). After parent(s)/caregiver(s)/legal guardian(s) have successfully administered IMP under close supervision of the Investigator at Visit 5-Visit 8 (Weeks 6, 8, 10, and 12), the Investigator may approve them to perform home administration of IMP at all further visits that do not require a scheduled clinic visit (ie, at Weeks 14, 18, 22, 26, 30, 34, 38, 42, 46, and 50). Patients should be monitored for 30 minutes after home administration of IMP. It is possible to start home administration at any visit following Visit 9, provided parent(s)/caregiver(s)/legal guardian(s) have been trained by the investigator or designee to administer IMP by demonstration

at not less than 3 visits followed by a successful IMP administration under close supervision of the investigator or designee at not less than 3 visits.

However, if parent(s)/caregiver(s)/legal guardian(s) do not develop the comfort to inject the IMP at home, or the Investigator determines that injection by parent(s)/caregiver(s)/legal guardian(s) at home is not appropriate, alternative arrangements may be made: for example for qualified site personnel and/or healthcare professionals (eg, visiting nurse service) to administer IMP at these timepoints at the patient's home.

For IMP doses not given at the study site, 'home dosing diary' (paper format) will be provided to record information related to the injections. Such home dosing diaries will be kept as source data in the patient's study file.

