Parent(s)/caregiver(s)/legal guardian(s) should be instructed to avoid missing any site visits (ie, IMP doses) or doses of background therapy during the study. For any patient who misses a site-visit (ie, IMP dose) or doses of background therapy, the parent(s)/caregiver(s)/legal guardian(s) should be reminded to be diligent to avoid missed visits and doses of background therapy thereafter.

The patient(s)/parent(s)/caregiver(s)/legal guardian(s) should continue their scheduled visits for IMP treatment (with study procedures, as detailed in [Section 1.2](#)), even if more than 2 consecutive doses of IMP are missed, or background medication was not taken by the patient(s) for up to 2-4 days.

The SC injection sites should be alternated among the 4 quadrants of the abdomen (avoiding navel and waist areas), the upper thighs or the upper arms, so that the same site is not injected twice consecutively. For each injection, the anatomic site of administration will be recorded in the electronic-case report form (e-CRF) or, as applicable, the home dosing diary.

Detailed instructions for transport, storage, preparation, and administration of IMP are provided to the patient and parent(s)/caregiver(s)/legal guardian(s). Parent(s)/caregiver(s)/legal guardian(s) will complete a dosing diary to document compliance with injection of IMP.

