11.4.1.2 Compliance

An administration is considered compliant if an injection is performed with the planned dose as required by the protocol. No imputation will be made for patients with missing or incomplete data. When an administration is given with a dose above the planned dose, the corresponding administration is defined as above-planned dose noncompliance. When an administration is given with a dose below the planned dose, the corresponding administration is defined as below-planned dose noncompliance. Percentage of treatment compliance, above-planned dose and below-planned dose non-compliance will be summarized descriptively (N, Mean, standard deviation [SD], Median, Min, and Max). The percentage of patients with compliance is <80% will be summarized.

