2.1.4 Safety endpoints

The safety analysis will be based on the reported adverse events and other safety information, such as clinical laboratory data, vital signs, ECG and physical exam.

Observation period

The observation period will be divided into 4 epochs:

The **screening** epoch is defined as the time from the signed informed consent date up to the first IMP administration.

The **treatment** epoch is defined as the time from the first administration of the IMP to the last administration of IMP + 14 days or till rollover to the LTS14424 study whichever is earlier.

The **residual treatment** epoch is defined as the time from the last administration of the IMP + 15 days to the last administration of IMP + 98 days or till rollover to the LTS14424 study whichever is earlier.

The treatment-emergent adverse event period will consist of the **treatment** and **residual treatment** epochs.

The **post-treatment** epoch is defined as the period of time starting the day after the end of the treatment-emergent adverse event period up to the end of the study (defined as last protocol-planned visit or the resolution/stabilization of all serious adverse events and adverse events with pre-specified monitoring).

The on-study observation period is defined as the time from start of treatment until the end of the study (defined as last protocol planned visit or the resolution/stabilization of all serious adverse events and adverse events with pre-specified monitoring).

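### The IMP compliance percentage drops most doses missed at the end of the course when a child is not recorded as permanently discontinued

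*SAP*

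**What the plan says.** SAP 2.4.3.2 (Compliance) defines a child's compliance as the number of compliant administrations divided by "the total number of administrations that the patient was planned to take during the treatment epoch defined in" SAP 2.1.4. The above-planned and under-planned dosing percentages use the same denominator. The section also reports the percentage of children with compliance below 80%.

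SAP 2.1.4 (Safety endpoints, observation period) defines the treatment epoch as running from "the first administration of the IMP to the last administration of IMP + 14 days or till rollover to the LTS14424 study", whichever comes first. The residual treatment epoch then runs from "the last administration of the IMP + 15 days to the last administration of IMP + 98 days", so day 14 after the last dose still belongs to the treatment epoch.

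Protocol 11.4.1.2 says what a compliant administration is but gives no denominator. It does plan the same summary: "The percentage of patients with compliance is <80% will be summarized". The SAP wording therefore decides the calculation.

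On dosing, Protocol 8.1.4 states: "The IMP is administered every 14 ± 3 days q2w". The flow chart footnote on IMP administration (Protocol 1.2) says that doses "must be separated by at least 11 days) up to Week 50". Protocol 10 ties the planned visit dates to the first injection. Protocol 8.1.4 keeps children in their scheduled IMP visits "even if more than 2 consecutive doses of IMP are missed", and Protocol 10.3.2 reserves permanent discontinuation for a definitive decision not to re-expose the child.

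**The concern.** A compliance percentage should compare what was taken with what was due. Here the last dose taken sets the end of the window in which doses are due. A gap followed by a later dose is counted as non-compliance, but the same gap at the end of the course mostly leaves the calculation.

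For a child whose permanent stop is recorded, this is simply compliance while on treatment. The gap concerns a child who misses a run of final doses without a recorded permanent discontinuation. The protocol allows for that, because missed doses alone do not amount to discontinuation. Such a child has no discontinuation reason in the disposition table, and the compliance table shows near-perfect adherence. At stake is the accuracy of a descriptive adherence summary, in particular the count of children below 80%.

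**Working it through.** The documents state no compliance figure, so there is none to reproduce.

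**Inputs**
- Planned doses: one every 2 weeks from Week 0 to Week 50 (Protocol 1.2 and 8.1.4), so 50/2 + 1 = 26.
- End of the treatment epoch: last dose + 14 days; the residual epoch starts at + 15 days (SAP 2.1.4).
- Planned dates anchored to the first injection (Protocol 10), dosing window ±3 days (Protocol 8.1.4).
- Threshold for low compliance: 80% (SAP 2.4.3.2).

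**How many trailing misses can count.** Suppose the last dose is given *d* days late, with *d* between −3 and 3. The next planned dose is then 14 − *d* days away.
- On time or 1 to 3 days late: 14 to 11 days away, inside the epoch, so it counts.
- 1 to 3 days early: 15 to 17 days away, outside the epoch, so it does not count.
- The second missed dose is 28 − *d* days away, at least 25, and never counts.

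So either no trailing missed dose counts or exactly one does.

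**Compliance for a child who takes the first *m* doses and misses the rest** (*m* below 26, no permanent discontinuation recorded): *m*/*m* if the next dose falls outside the epoch, *m*/(*m* + 1) if inside, and *m*/26 against the planned schedule.

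| Doses taken | SAP, next dose outside | SAP, next dose inside | Planned schedule |
|---|---|---|---|
| 3 | 100% | 3/4 = 75.0% | 3/26 = 11.5% |
| 4 | 100% | 4/5 = 80.0% | 4/26 = 15.4% |
| 13 | 100% | 13/14 = 92.9% | 13/26 = 50.0% |
| 20 | 100% | 20/21 = 95.2% | 20/26 = 76.9% |
| 21 | 100% | 21/22 = 95.5% | 21/26 = 80.8% |

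**The 80% summary.** On the planned schedule, *m*/26 is below 0.80 when *m* is below 20.8, that is for *m* up to 20. Under the SAP, *m*/(*m* + 1) is at least 0.80 once *m* is 4 or more. A child with this pattern and 4 to 20 doses taken is below 80% of the schedule but outside the summary under either treatment of day 14.

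**Mixed pattern.** Three doses missed mid-course and the last three missed leaves 20 taken. The SAP gives 20/23 = 87.0% or 20/24 = 83.3%, against 20/26 = 76.9%. The child again crosses the threshold.

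**Home doses only.** A child misses the home doses at Weeks 42, 46 and 50 but is dosed at the clinic visits at Weeks 44 and 48 (Protocol 10.1.10). The Week 42 and 46 misses precede later doses and count. Week 50 is 14 days after an on-time Week 48 dose and counts too. The SAP gives 23/26 = 88.5%, the same as the planned schedule.

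**The case against.** The strongest reply is that this is a coherent on-treatment measure and that early stopping is shown elsewhere. The protocol prescribes no denominator. SAP 2.4.3.1 reports exposure duration from the last dose date, whether or not discontinuation was recorded: a child whose last dose is the 20th, at Week 38, shows 38 + 2 = 40 weeks. SAP 2.2 counts children who did not complete the 52-week treatment, as well as permanent discontinuations by reason. Protocol 10.3 and 10.3.4 require IMP discontinuations to be documented in the e-CRF, which should leave few children with a long undosed tail and no record. All of this stands. It settles the case of formal discontinuers and limits the size of what remains. It does not make the compliance figure right for a child still due for doses, and SAP 2.4.3.2 does not label the measure as on-treatment.

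A reader might infer more than the documents support:
- *That doses missed at the end never count.* One can, because day 14 is inside the epoch.
- *That skipping the late home doses is enough to hide them.* It is not, because the clinic doses at Weeks 44 and 48 bring them inside the epoch. A long uncounted tail requires missed on-site doses as well.
- *That the treatment-adherence estimand is affected.* SAP 2.4.4.1 does not use the compliance percentage. It takes events and duration from the treatment epoch itself, up to any permanent regimen change, so an undosed tail beyond 14 days is already outside it.
- *That the 20% discontinuation assumed for the sample size measures the affected group.* That is an assumption about discontinuation, whereas this point concerns children with no recorded discontinuation.

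**Conclusion.** The point holds in a limited form. For a child not recorded as permanently discontinued who misses a run of final doses, the second and later misses drop out of the denominator. Compliance is then overstated against the planned schedule, by 18 to 23 percentage points at 20 doses taken (95.2% or 100% against 76.9%), and the child can be left out of the summary below 80%.

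This assumes 26 planned doses, planned dates fixed from the first injection, and a last dose given within the ±3-day window. The number of such children is not in the documents and is probably small. The summary is descriptive, and no efficacy test, analysis population or estimand uses it. It is a cheap improvement and does not threaten the trial's conclusions.

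**What to change.** In all three percentages of SAP 2.4.3.2, replace the reference to the treatment epoch with: *from the first dose to the earlier of the recorded date of permanent IMP discontinuation (or study withdrawal) and the scheduled Week 50 administration*.

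The child with 20 doses and no recorded stop is then reported at 20/26 = 76.9% and enters the summary below 80%. A child formally discontinued is still judged only on the time before the stop. The dependence on whether the last dose was a day early or late disappears.

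The cost is one changed derivation and a slightly less favourable compliance figure. The epoch definition in SAP 2.1.4 and the safety and efficacy analyses that use it stay as they are.
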